## 17 Insurance and Liability

### 17.1 Subject Compensation

The sponsor agrees to abide by the Medical Technology Association of Australia Guidelines for compensation for injury resulting from participation in a company sponsored clinical investigation.

	QMS Template	Doc ID: RMI-ROBOTECHO-CIP-002 Ver No: V2.0
	Clinical Investigation Protocol	

## 17.2 Insurance Indemnity

The Sponsor will have in place Clinical Trial Insurance (with a \$20m limit) and ensure that the investigational site/entity has in place Indemnity according to Medical Technology Association of Australia Form of Indemnity for Clinical Investigations.

## 17.3 Compliance with Good Clinical Practice

The clinical investigation will be conducted in accordance with the clinical investigation plan, the ethical principles of the Declaration of Helsinki, the principles of IS-EN ISO 14155:2020 and current national regulations governing this clinical investigation. This is to ensure the safety and integrity of the subjects and the quality of the data collected.

## 17.4 Archiving and Regulatory Inspection

The PI and sponsor will maintain the essential clinical investigation documents in the Sponsor Trial Master File and investigation site files archive. The sponsor shall keep all documentation for at least 15 years or as long as stipulated by the local institution.

## 18 Study Report

A clinical study report will be prepared and provided to the study investigator irrespective of whether the study terminates prematurely. A report may be used to support regulatory approval applications. The report will meet the standards of the ICH Guideline for Structure and Content of Clinical Study Reports.

## 19 Publication of Results

The clinical investigation will be registered in a publicly accessible database anzctr.org.au before the start of recruitment activities and the content will be updated throughout the conduct of the clinical investigation and the results entered at completion of the clinical investigation.

All information concerning the RUAT Echo study, operations, manufacturing, and clinical data which are not previously published are considered confidential by RMI Oceania Pty Ltd and shall remain the sole property of RMI Oceania Pty Ltd. Investigators must respect the confidentiality of data. The investigator should understand that the information developed in the clinical study will be used by RMI Oceania Pty Ltd in connection with the evaluation of the RUAT Echo system, and therefore may be disclosed as required to other clinical investigators, and to governmental agencies.

Should the investigators wish to publish, exhibit or lecture on the results of this study, the manuscript, exhibit, or presentation must be provided to RMI Oceania Pty Ltd at least 40 days prior to the intended use of the data as per the Clinical Investigation Research Agreement. For the avoidance of doubt, the investigator must receive written consent from RMI Oceania Pty Ltd prior to publication, exhibition, or disclosure of scientific and clinical data. This review by RMI Oceania Pty Ltd is not intended to curtail distribution of scientific and clinical data, but to identify and edit any company confidential information.

Authorship and publication manuscript composition will reflect joint-cooperation between multiple investigators, sites, RMI Oceania Pty Ltd personnel and delegates. Authorship will be established prior to writing any publications and adhere to NHMRC Authorship guide document R41C; Authorship: Guidance supporting the Australian. Code for the Responsible Conduct of Research, 2019.

	QMS Template	Doc ID: RMI-ROBOTECHO-CIP-002 Ver No: V2.0
	Clinical Investigation Protocol	

## 20 Conflict of Interest Declarations

Conflicts of interest (COI) are defined as per Chapter 5.6 of the *National Statement on Ethical Conduct in Human Research (2023)* and the *Australian Code for the Responsible Conduct of Research (2018)* and are required to be disclosed in relation to researchers of the clinical study.

### 20.1 Investigator Declaration

[name], Director of Cardiac Sciences, Cardiac Investigations Unit, Royal Brisbane Women’s Hospital is a co-investigator of this study and declares a conflict of interest (COI). [name] is a Director, and shareholder of the Sponsor company RMI Oceania Pty Ltd with financial and intellectual property interests.

[name] has contributed intellectually to the design of both the medical device and the clinical trial.

To manage the COI [name] **will not**:

- Be involved in identification of patient participants,
- Consent patients for the study,
- Conduct RUAT scans or manual echo scans,
- Interact with patient participants,
- Record or access clinical study data during the trial,
- Record or review safety events.

## 21 Sponsor and Investigator Obligations

### 21.1 Protocol Amendments

Neither the investigator nor the sponsor will modify or alter this protocol without the agreement of the other. All agreed protocol amendments will be clearly recorded on a protocol amendment form and will be signed and dated by the original protocol approving signatories. All protocol amendments will be submitted to the relevant institutional HREC for approval before implementation. The only exception will be when the amendment is necessary to eliminate an immediate hazard to the trial subjects. In this case, the necessary action will be taken first, with the relevant protocol amendment following shortly thereafter.

### 21.2 Protocol Deviations

Investigator(s) are not allowed to deviate from the CIP except if it is for the protection of the subject’s rights, safety, or well-being under emergency circumstances. All deviations shall be documented and reported to the sponsor, and the Ethics Committee as soon as possible. Deviations will be reviewed by the sponsor and reported to the appropriate regulatory bodies as required.

### 21.3 Investigator Responsibilities

The investigator must ensure that the study is conducted in accordance with the study protocol, study agreement, HREC approval and all appropriate regulatory guidelines including ICH GCP and ISO 14155.

#### 21.3.1 Progress Reports

The investigator will submit, at intervals requested by the sponsor, a progress report on this investigation. These reports will be submitted both to the sponsor and to the investigator’s Ethics Committee.

	QMS Template	Doc ID: RMI-ROBOTECHO-CIP-002 Ver No: V2.0
	Clinical Investigation Protocol	

### 21.3.2 Withdrawal of Ethics Committee Approval

Should the Ethics Committee withdraw its approval, the investigator will notify the sponsor no later than five working days following such withdrawal.

### 21.3.3 Final Reports

Upon completion of the investigation, each investigator will contribute to submitting a final report on his/her part of the investigation within three months of completion of the investigation. This report will be submitted both to the sponsor and the investigator's Ethics Committee.

## 21.4 Sponsor Responsibilities

### 21.4.1 Reports

The sponsor, upon completion of the investigation, will prepare a comprehensive final report. These reports will be submitted to the investigator and the investigator's Ethics Committee.

### 21.4.2 Clinical Monitoring of the Study

The sponsor will monitor and ensure that this investigation is conducted in accordance with the signed investigator clinical study agreement and conditions imposed by the Ethics Committee, as well as other applicable regulations, including ICH GCP and ISO 14155.

## 23 Appendices

### 23.1 APPENDIX 1 - Functional Verification Checklist

#	Function	Performs as Intended (Y/N)
1	Did the Robotic Arm & cameras activate when turned on?	
2	Did the robotic arm move into home position when instructed?	

3	Did the robotic arm move into the preset positions correctly?	
4	Could the sonographer move the robotic arm onto the patient's chest from each preset position?	
5	Could the sonographer move the robotic arm from the end of the preset movement to the correct location on the patient's chest? (tests x,y, z axes).	
6	When in the correct location, could the robotic arm be instructed to the correct angulation so that an image could be acquired? (tests panning, tilting, rotation functionality).	
7	Did the force sensor work within its pressure range?	
8	Did the probe holder hold the probe correctly for the scan?	
9	Was there any restriction to the robotic arm movement caused by the cables? (wound around arm, caught in the bed, too short length from the US machine).	
10	Could the sonographer move the robot trolley as required during the scan?	
11	Did the patient telehealth screen provide adequate image and audio?	
12	Was the sonographer satisfied that the images could be used for reporting?	

	QMS Template	Doc ID: RMI-ROBOTECHO-CIP-002 Ver No: V2.0
	Clinical Investigation Protocol	

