## 10.2.1 Evaluation

### 10.2.1.1 Functional verification of RUAT ECHO

The *Observing Sonographer* will complete a functional verification checklist (see APPENDIX 1 - Functional Verification ) to verify that the RUAT echo was performed as intended (as described in the Instruction Manual).

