#### 11.1.1 Decision Criteria

The primary objectives of the study are to:

- assess the **safety** of the RUAT echo.
- assess the **“useability” (functionality)** of using the RUAT echo as intended to obtain echocardiogram images of clinically suitable quality for reporting by a cardiac sonographer.

The **safety** of the RUAT Echo will be considered acceptable if there are no device related adverse effects.

RUAT Echo will be considered a **useable** method of performing echocardiograms if:

- Each functional verification criteria 1 through 11 (inclusive) performed “YES” at least 80% of the time an echocardiogram was performed by RUAT Echo, that is, pass functional verification (see APPENDIX 1 - Functional Verification ).
- At least 80% of echocardiograms performed by RUAT Echo are considered of an adequate quality to provide a diagnostic assessment, that is, pass functional verification item #12 (see APPENDIX 1 - Functional Verification ).
- At least 80% of participants report they are satisfied with undergoing RUAT Echo examination based on an average of the 4 subscales of the 10-point Likert scales from strongly disagree to strongly agree (see APPENDIX 2 – Participant Survey).

	QMS Template	Doc ID: RMI-ROBOTECHO-CIP-002 Ver No: V2.0
	Clinical Investigation Protocol	

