### 11.3.2 Useability (functionality)

The RUAT Echo device will be deemed as being **sufficiently useable (functional)** (i.e., technically non-inferior) **if each of the 12 Functional Verification Criteria** (see APPENDIX 1 - Functional Verification ) result in "YES"  $\geq 80\%$  of the time.

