#### 11.6 Sample Size Determination

Approximately 30 participants will be recruited. A single-group design will be used to obtain a two-sided 95% confidence interval for a single proportion of the RUAT Echo images that are deemed of sufficient quality. The Exact (Clopper-Pearson) formula will be used to calculate the confidence interval. The sample proportion is assumed to be 80%. With a sample size of 30, the width of the associated confidence interval is 30.9% around the 80% (that is, from 61.4% to 92.3%).

Confidence interval widths were computed using PASS 2023, version 23.0.2.

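### Checklist item 9 is worded in the opposite direction to the other 11 items and its scoring direction is not stated, so the 80% YES rule inverts if the item is answered as worded

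*Protocol*

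**What the plan says.** Appendix 1 (Protocol 23.1) is a 12-line checklist with one answer column, headed "Performs as Intended (Y/N" (closing bracket omitted here). Items 1 to 8 and 10 to 12 ask whether something worked, so yes is favourable. Item 9 asks "Was there any restriction to the robotic arm movement caused by the cables" and gives examples of cable faults, so the favourable answer to the question itself is no.

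Section 10.2.1.1 has the Observing Sonographer complete the list "to verify that the RUAT echo was performed as intended".

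Two sections turn the answers into a decision:

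- Section 11.1.1: "Each functional verification criteria 1 through 11 (inclusive) performed “YES” at least 80% of the time an echocardiogram was performed by RUAT Echo". Item 12 and participant satisfaction each have a separate 80% rule.
- Section 11.3.2 calls the device sufficiently useable "if each of the 12 Functional Verification Criteria" come out as YES at least 80% of the time.

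Neither section exempts item 9 or says that its score is reversed. Useability is one of the two primary objectives.

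**The concern.** For eleven items, the answer to the question and the answer to the column heading are the same letter. For item 9 they are opposite letters. An observer whose cables ran free can reasonably write N (there was no restriction) or Y (the function performed as intended), and nothing on the form or in the decision rule says which is wanted.

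The consequences differ in direction. Because the rule needs every item to pass, a false failure on item 9 is enough to fail the useability objective for a sound device. A false pass does not establish useability by itself, since the other criteria must still be met, but it removes the only check aimed at cable restriction. Inconsistent answering across observers would make the item 9 percentage hard to interpret in either direction.

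**Working it through.** **The plan's own figure.** Section 11.6 gives a Clopper-Pearson 95% interval for 80% with 30 participants of 61.4% to 92.3%, width 30.9%. Beta quantiles for 24 of 30 give 61.43% to 92.29%, width 30.85%, so it is reproduced. That interval concerns image quality (item 12) and is not affected by this point.

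**Inputs.**
- Number of scans: 30 (Section 11.6: "Approximately 30 participants will be recruited").
- Pass mark: 80% (Sections 11.1.1 and 11.3.2), that is 0.80 × 30 = 24 YES.
- True cable-restriction rate r: not given in the Protocol. It is assumed here and varied from 0% to 100%.
- Share m of forms answered as worded: not given; varied.

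**Formula.** With X the number of YES answers, P(pass item 9) = P(X ≥ 24) = Σ C(30,k) p^k (1−p)^(30−k) for k = 24 to 30. Scans are taken as independent. If the question is answered as worded, p = r. If Y means performs as intended, p = 1 − r.

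| Assumed r | P(pass), answered as worded | P(pass), under the column heading |
|---|---|---|
| 0% | 0 | 1.000 |
| 5% | 2.6e-26 | 0.999 |
| 10% | 3.2e-19 | 0.974 |
| 20% | 2.8e-12 | 0.607 |
| 50% | 0.0007 | 0.0007 |
| 80% | 0.607 | 2.8e-12 |
| 90% | 0.974 | 3.2e-19 |
| 100% | 1.000 | 0 |

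The two columns are mirror images. The same physical performance gives opposite results, depending only on how the observer reads the line.

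**Mixed reading.** If a share m of forms is answered as worded and the rest under the heading, p = m·r + (1−m)(1−r).

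| m | p at r = 0% | P(pass) at r = 0% | p at r = 5% | P(pass) at r = 5% |
|---|---|---|---|---|
| 10% | 0.90 | 0.974 | 0.86 | 0.883 |
| 20% | 0.80 | 0.607 | 0.77 | 0.447 |
| 33% | 0.667 | 0.084 | 0.65 | 0.059 |
| 50% | 0.50 | 0.0007 | 0.50 | 0.0007 |

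A count shows the same thing. With cables that never restrict the arm, each form answered as worded is a NO. Six such forms leave 30 − 6 = 24 YES and the item just passes; a seventh leaves 23 and it fails.

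**The case against.** The strongest reply is that the form already supplies the direction. Its only answer column asks about intended performance, Section 10.2.1.1 describes the purpose of the checklist in the same terms, and Section 11.1.1 speaks of each criterion being performed and of passing functional verification. Read that way, Y on item 9 means no restriction and the rule behaves correctly. This reading is at least as well supported as the plain one. A reader might infer that the plan necessarily fails a faultless device and passes a faulty one. The documents do not support that: it follows only if the question is answered as worded.

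A reader might also infer that inconsistent answers could never be sorted out. That goes too far. Section 15.3 provides for source review and on-site correction of case report forms, Section 15.4 has the investigator or coordinator verify entries, and there are only about 30 forms at one site. Queries are feasible, though they depend on what the observer remembers.

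Finally, Section 11 leaves technical detail to an SAP finalised before database lock, and that SAP could say which answer passes. This would settle the scoring but not the data: a later rule cannot show what each observer meant by Y. The study is also a descriptive single-arm pilot, which limits the consequences of one item.

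What survives is that the heading and the question ask for opposite letters on one line, and the Protocol does not resolve this where the answer is recorded.

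**Conclusion.** The point stands as an ambiguity in a primary decision criterion, not as a certain inversion. Item 9 is reverse-worded, the YES rule covers it without exception, and the scoring direction is unstated. Consistent answers under the column heading do no harm. Consistent answers to the question as worded invert the rule completely. Between these, the result is sensitive to modest inconsistency: with faultless cables, one fifth of forms answered as worded cuts the chance of passing to 0.607 and one third cuts it to 0.084.

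These figures rest on 30 completed scans, independence between scans, and assumed restriction rates and answering patterns, none of which the Protocol provides. They show how the rule behaves; they do not predict the trial's result.

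**What to change.** Before the first scan, reword item 9 so that YES is favourable, for example: *Was the robotic arm free of any restriction caused by the cables?* The question and the column heading then agree, Sections 11.1.1 and 11.3.2 can stay as they are on this point, and the pass probabilities are those in the right-hand column of the first table.

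If forms are already in use, state in both 11.1.1 and 11.3.2 which answer to item 9 counts as a pass, and query each completed form for how the observer coded it, recording the query and accepting that recall is imperfect.

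The cost is one line on a paper form, handled through the Protocol's amendment procedure. No extra participants, scans or data are needed. The later remedy costs up to about 30 queries and is less reliable.

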## 23.2 APPENDIX 2 – Participant Experience Survey

### Study Title:

Safety and useability of a novel robot-assisted echocardiographic examination – The RUAT ECHO Study – Medical Device Clinical Trial

**Principal Investigator:** [name]

Director of Cardiology and Senior Staff Cardiologist,

Cardiology, Royal Brisbane and Women’s Hospital

[[contact]](mailto:[contact])

**Study Coordinator:** [name]

Research Fellow, Research Manager, Program Manager,

Cardiology, Royal Brisbane and Women’s Hospital

[[contact]](mailto:[contact])

This survey has been provided to you as you have consented to participate in the **RUAT (ROBOT) ECHO study** and have undergone a robot cardiac ultrasound (also known as echocardiogram or ‘echo’). The following statements for you to provide are to investigate patient experiences regarding the RUAT echo procedure.

*Questions to be asked by research team (not the operating sonographer) to the patient.*

Thank you for agreeing to participate in this study. Please respond to the questions below on a 10-point scale of your level of comfort with the procedure.

1. Were you comfortable (and lacking concern) with the speed of the automatic movements when the probe was not on your chest?									
On a scale of 1 to 10 with 1 being extremely uncomfortable and 10 being extremely comfortable where does your experience sit on this scale?									
1	2	3	4	5	6	7	8	9	10
2. When the sonographer was actively adjusting the probe on your chest, did you feel safe?									
On a scale of 1 to 10 with 1 feeling extremely unsafe and 10 feeling extremely safe where does your experience sit on this scale?									
1	2	3	4	5	6	7	8	9	10

3. Were you comfortable with the pressure applied by the robot to the chest?									
On a scale of 1 to 10 with 1 being extremely uncomfortable and 10 being extremely comfortable where does your experience sit on this scale?									
1	2	3	4	5	6	7	8	9	10
4. Could you clearly see the video of the sonographer?									
On a scale of 1 to 10 with 1 being unable to see the video at all and 10 being able to clearly see the video unobstructed where does your experience sit on this scale?									
1	2	3	4	5	6	7	8	9	10

5. Do you wish to receive by email a layperson summary of the clinical trial results?"

*If yes, you understand that you are consenting to be contacted via email for the sole purpose of providing study results. Your information will not be used for any other purpose.*

Please provide email if consenting: \_\_\_\_\_

- End of patient survey -

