
End-user (Sonographer & Patient) evaluation to understand if the selected technology is well-received
	
Most volunteers expressed some discomfort with the robot in the subcostal position. The discomfort was due to the continuous pressure applied on the belly and/or the feeling of being "imprisoned" under the robotic arm. One volunteer reported discomfort in the apical position due to the pressure on the ribs. In general, some volunteers expressed some stress/fear while being scanned, but none of the
	
Under review
	
There have been continuous positive responses received from both the sonographers and the patients with respect to the remote scan experiences over the evolution of the different device combinations used

	volunteers was contrary to the future use of a fully automated system for this type of scan. In general, the system was well received by the sonographers, who provided some suggestions to further improve the system		
--	--	--	--

Elements Analysed	Franka Panda Device (POC)	RUAT Device	Conclusions
Controllers	A touch haptic controller and a Logitech F710 controller were connected to the POC system. Sonographers were trained on the touch controller as it provides haptic feedback with 6 degrees of freedom (DOF). However, during the volunteer scanning, it was clear that the touch controller was considered challenging to operate. Moreover, movements requiring both translation and rotation pose a challenge with the touch controller. Controllers, which allow operation with both hands, might be easier to use and may have less of an impact on the sonographer	Logitech F310 Controller has been used. The controller allows the sonographer to manipulate the position of the probe, by sending commands to the robotic arm via the two NUCs (next unit of computing, i.e., minicomputer). Wired controllers were chosen due to having a more reliable connection and not being reliant on batteries.	Use of the Logitech Controller (Gamepad) in combination has resulted in better arm maneuverability and more effective scanning using the RUAT device

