	QMS Template	Doc ID: RMI-ROBOTECHO-CIP-002 Ver No: V2.0
	Clinical Investigation Protocol	

	actions, provide the sonographer with messaging, and possible options aiming at improving remote scanning	
while looking at the ultrasound image. This adjustment may include increasing the applied force, adjusting the angle relative to the body, or moving the probe along the surface of the body.
 
4. Once the sonographer has obtained the desired images, they will switch to velocity mode, and move the probe away from the body.
 
5. When a sufficient distance has been reached (minimum 10cm), the sonographer selects another scan window from the display and repeats the above process.
	
Robot selected	A Franka Panda robot was used for the POC system. However, it will be necessary to test a range of robots to assess their capability, DOF (including their singularities), software capability, force and torque control, human safety, etc.	
Kinova Jaco2 robotic arm over the Kuka MED7. The comparison between the two arms is as follows:
 
 
• DOF of a robotic arm refers to the number of joints (composed of “wrists” and “elbows”) available to help move the end effector. A minimum of 6 joints is required to ensure the arm can be manipulated completely in space (3 translational directions and 3 rotational directions), however a 6-DOF arm will have some areas within which joints begin to align and the solution becomes unstable. These locations are referred to as “singularities”. Adding an additional joint (going from 6-DOF to 7-DOF) can reduce the level of instability and is generally preferred to ensure smooth movement of the end effector.
 
	
Through the availability of 6-DoF from using the Jaco2 arm, effective manipulations through multiple directions have enabled the sonographers to perform effective scans.
 
A recommendation is made to consider the 7-DOF version of the Kinova robotic arm for future development to further extend the device capabilities

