### 10.1 Administrative and Screening Procedures

#### 10.1.1 Screening and Recruitment

Prior to enrolment in the study, each participant will have already received a routine (manual) clinically reportable echocardiogram as an inpatient or outpatient.

Potential study participants will be selected based on inclusion and exclusion criteria, as above.

The potential study participant will be approached in person via a member of the study team (study coordinator or research staff as delegated by the principal investigator) while on the ward as an inpatient or in clinic as an outpatient. The study coordinator or research staff will provide details of the study (verbally and via the information sheet as part of the Participant Informed Consent Form 'PICF'), as outlined in Section 16.2.

At the time of informed consent potential study participants will be asked to disclose any bruising, soreness, or discomfort in the chest area that may impact safety outcomes that the RUAT study may have.

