**Risk: Study Participant discomfort due to pressing of ultrasound probe on chest (Robot-assisted Ultrasound Examination)**

Mitigation: Participants will be informed of the potential for slight discomfort on the chest from pressing the ultrasound probe and that they can discontinue participation at any point if they find the pressure from the probe too uncomfortable to continue participation. The robot has an active pressure sensor with a limiter to prevent excess pressure being applied. The pressure limit is set to approximately 50% of the maximum pressure exerted by a human operator performing a standard ultrasound examination. A blue LED light on the sensor confirms pressure signals are actively being received and in the event of sensor failure, the pressure reading will drop to zero. Daily checks of the system include a manual test of the

	QMS Template	Doc ID: RMI-ROBOTECHO-CIP-002 Ver No: V2.0
	Clinical Investigation Protocol	

pressure sensor which requires applying gentle pressure to the probe holder and the sonographer is to confirm that the force indicator moves on the computer display for every force limit level (1-5).

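### The participant survey asks about probe pressure and safety only on the chest, although the sponsor's earlier testing found discomfort mainly in the subcostal position

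*Protocol*

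**What the plan says.** Participant experience is one of the primary endpoints (Protocol Table 2). Section 11.1.1 requires at least 80% of participants to be satisfied, judged on the average of four 10-point survey scales.

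The four scored items in Appendix 2 are:

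- Item 1: "Were you comfortable (and lacking concern) with the speed of the automatic movements when the probe was not on your chest"
- Item 2: feeling safe while the probe is adjusted on the chest.
- Item 3: "Were you comfortable with the pressure applied by the robot to the chest"
- Item 4: whether the video of the sonographer could be seen.

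Item 5 only offers a results summary by email. Section 10.2.1.2 says that the survey also invites free comment and a preference between manual and robotic scanning. Neither is on the form.

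Table 1 (Section 5.1) gives the proof-of-concept experience: "Most volunteers expressed some discomfort with the robot in the subcostal position". It continues: "The discomfort was due to the continuous pressure applied on the belly", and/or to a sense of being shut in under the arm. By contrast, "One volunteer reported discomfort in the apical position due to the pressure on the ribs".

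The risk text in Section 12 is limited to the chest: "Participants will be informed of the potential for slight discomfort on the chest from pressing the ultrasound probe". At consent, Section 10.1.1 has participants "asked to disclose any bruising, soreness, or discomfort in the chest area". Footnote 2 to the Schedule of Assessments (Section 4) also records bruising or soreness at that stage, but names no body site.

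**The concern.** The protocol reports where an earlier version of this technology was uncomfortable, and its questionnaire then names a different place. A lay respondent asked about the chest would reasonably leave out the belly. Someone bothered by pressure below the ribs, or by lying under the arm, could answer all four items favourably and truthfully. The satisfaction criterion could then be met without having examined the main complaint in the sponsor's own testing. With no comment field, the form has no other place to record it.

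The baseline has a smaller version of the same problem. If soreness before the scan is asked about only in the chest area, upper-abdominal soreness after the scan has no comparator.

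**Working it through.** **The plan's own figure.** The only sample-size calculation (Section 11.6) concerns image quality, not comfort. For 24 of 30, the Clopper-Pearson limits are the 2.5% quantile of Beta(24, 7) and the 97.5% quantile of Beta(25, 6). They come to 61.43% and 92.29%, width 30.85 points, which agrees with the stated 61.4% to 92.3% and 30.9%. The present point does not depend on it.

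**Site named in each place.**

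| Place in protocol | Site named |
|---|---|
| Table 1, proof-of-concept discomfort | Subcostal position, belly (most volunteers); ribs (one volunteer) |
| Appendix 2, item 2 (safety) | Chest |
| Appendix 2, item 3 (pressure) | Chest |
| Section 12, discomfort risk | Chest |
| Section 10.1.1, question at consent | Chest area |
| Section 4, footnote 2, bruising or soreness | None |
| Section 10.2.1.2, description of survey | None (probe pressure in general) |
| Sections 10.3.1 to 10.3.4, adverse events | None |

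Item 1 does not fill the gap. It concerns the speed of automatic movements, whereas Table 1 describes the sonographer taking manual control to make contact and apply force.

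**Effect on the survey average.** The score is the sum of four items divided by 4.

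- Subcostal discomfort, items read literally: (10 + 10 + 10 + 10)/4 = 10.
- Same participant, item 3 reworded and scored 1: (10 + 10 + 1 + 10)/4 = 7.75.
- Same participant, items 2 and 3 both reworded and scored 1: (10 + 1 + 1 + 10)/4 = 5.5.
- Same participant, a separate fifth item added instead and scored 1: (4 × 10 + 1)/5 = 8.2.

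Rewording therefore makes the discomfort visible, and dilutes it less than a fifth item would. Whether 7.75 or 5.5 counts as satisfied cannot be said, because the protocol gives no cut-off.

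**How many might be affected.** The rate with the RUAT is not in the document, so the rates below are assumptions. The expected number is 30p, and the chance of at least one affected participant is 1 − (1 − p)^30.

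- p = 5%: 1.5 expected; chance 78.5%.
- p = 10%: 3 expected; chance 95.8%.
- p = 20%: 6 expected; chance above 99%.
- p = 50%: 15 expected; chance above 99%.

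For scale, 80% of 30 is 24, so the criterion tolerates 6 participants who are not satisfied.

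**The case against.** The strongest reply is that the discomfort is captured elsewhere. Adverse events are a separate primary endpoint. Their definition covers any undesirable symptom (10.3.1), collection runs from consent to 72 hours after the scan (10.3.2), questioning is open-ended (10.3.3), and discomfort and probe pressure are listed as procedure-related examples with no site (10.3.4). This stands. A reader might infer that subcostal discomfort goes unmeasured altogether, or that the rule of no device-related effects is biased towards success. The documents support neither. What remains is that this route relies on what participants volunteer, while the survey is the structured instrument and does not ask.

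The evidence behind the concern is also thin. "A Franka Panda robot was used for the POC system", whereas the trial device uses a different arm, with a limiter set at about half the maximum pressure of a manual operator (Section 12). Table 1 gives no count of volunteers asked about comfort. The scans it describes for the second training session amount to at most 3 + 3 + 2 = 8 volunteer scans. The discomfort was described as partial, and no volunteer opposed future use of such a system. All of this stands, and it means that the RUAT rate is unknown.

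Nor is Table 1's proof-of-concept cell the only patient evidence. Its conclusions column reports favourable responses from patients, and Section 5.2 describes 78 people scanned on the near-final device, with a statement that this can be done safely. Neither gives comfort by scan position, and the RUAT cell on patient evaluation is marked as under review.

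Finally, the protocol lists no scan windows, and Appendix 1 item 4 speaks of the chest for every preset position. Chest may be shorthand for any contact site, or the subcostal window may not be used. Shorthand would explain the wording, but a participant filling in the form would not know it.

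**Conclusion.** The mismatch is real and modest. Provided the subcostal window is scanned, the survey behind a primary criterion does not specifically measure the discomfort most often reported in the sponsor's earlier testing, and the promised free-text route is missing from the form. At the extreme, an affected participant scores the maximum average of 10.

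This rests on two assumptions: that a full echocardiographic examination here includes the subcostal window, and that participants read chest literally. The number affected cannot be estimated from the document.

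The missing-baseline point is narrower than it may appear. Section 10.1.1 limits the question to the chest area, but footnote 2 in Section 4 does not, so the two need reconciling; it does not follow that no abdominal baseline would be recorded. Section 12 is a summary that refers to the Investigator's Brochure, which is not at hand, so the comment on it concerns its wording only.

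**What to change.** - Appendix 2, item 3: ask about *pressure applied by the robot to the chest or upper abdomen (all scan positions, including below the ribs)*.
- Appendix 2, item 2: replace the reference to the chest with *adjusting the probe on your body*.
- Appendix 2: restore the open-comment field described in Section 10.2.1.2, so that feeling trapped under the arm can be recorded.
- Reconcile Section 10.1.1 with footnote 2 in Section 4, so that the soreness recorded at baseline includes the upper abdomen.
- Align the discomfort wording in Section 12 with the above.

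Adverse event questioning should stay as it is. Prompting for events after a low survey score would sit badly with the non-leading approach in Section 10.3.3 and would change how a primary endpoint is ascertained.

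The cost is a wording change to the survey and two protocol sections, with any matching change to the participant information. There is no added visit and no effect on sample size. The downside is that satisfaction figures may look slightly less favourable.
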